9.6 Suicidality Data

Suicidality will be monitored during the study using the C-SSRS and will be summarized as number and percentage of subjects reporting any suicidal behavior, ideation, behavior by type (4 types), ideation by type (5 types) and treatment emergent suicidal behavior and ideation.

SAP 405-201-00014

Summary will be provided for the single-blind placebo run-in period and the double-blind treatment period for the Safety Sample.

Suicidality is defined as report of at least one occurrence of any type of suicidal ideation or at least one occurrence of any type of suicidal behavior during assessment period (count each person only once).

Treatment emergent suicidal behavior and ideation is summarized by four types: Emergence of suicidal ideation, Emergence of serious suicidal ideation, Worsening of suicidal ideation, Emergence of suicidal behavior.

Emergence of suicidal behavior/ideation is defined as report of any type of suicidal behavior/ideation during treatment when there was no baseline suicidal behavior/ideation.

Emergence of serious suicidal ideation is defined as observation of suicidal ideation severity rating of 4 or 5 during treatment when there was no baseline suicidal ideation.

Worsening of suicidal ideation is defined as a suicidal ideation severity rating that is more severe than it was at baseline.

For the double-blind treatment period analyses, the last available measurement prior to the first dose of double-blind IMP is being used as “Baseline”.

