Protocol 405-201-00014

Table 3.7-1 Schedule of Assessments - Screening Through End of Treatment										
Period	Screening ^a	PBO Run-in ^b	Double-blind Treatment							NOTES
			Baseline Day -1	Day 7 +1 Day	Day 14 ±2 Days	Day 21 ±2 Days	Day 28 ±2 Days	Day 35 ±2 Days	Day 42/ET ±2 Days	
Visit	1	2	3	4	5	6	7	8	9	
UDS/alcohol testing via breathalyzer or blood	X	X	X	X	X	X	X	X	X	Section 3.7.5.2
C-SSRS	X	X	X	X	X	X	X	X	X	Section 3.7.5.5.2
PHARMACOKINETIC/PHARMACOGENOMIC										
PK blood sample				X	X		X		X	Section 3.7.6.1
Pharmacogenomic and FBR samples			X							Section 3.7.6.2 Section 3.7.6.3
EXPLORATORY										
AIM-A		X	X				X		X	Section 3.7.3.1
ASRS	X	X	X				X		X	Section 3.7.3.4
OTHER										
IMP/placebo dispensing		X	X	X	X	X	X	X	X	
IMP/placebo return and accountability			X	X	X	X	X	X	X	Section 8.4 Section 3.12

anti-HCV = hepatitis C antibodies; FBR = future biospecimen research; HBsAg = hepatitis B surface antigen; HIV = human immunodeficiency virus;
UDS = urine drug screen.

^aScreening will include a washout period that can range from 7 to 28 days

^bSee [Section 3.7.1.2](#)

Protocol 405-201-00014

Table 3.7-2 Schedule of Assessments - Follow-up							
Period	Follow-up ^a						NOTES
	1 (+1) day after the last dose of IMP	2 (+1) days after the last dose of IMP	3 (+1) days after the last dose of IMP	5 (+1) days after the last dose of IMP	7 (+2) days after the last dose of IMP	10 (+2) days after the last dose of IMP	
Visit	10	11	12	13	14	15	
ENTRANCE/HISTORY							
Concomitant medication(s)	X	X	X	X	X	X	
EFFICACY							
AISRS		X			X		Section 3.7.2.1
SAFETY							
Adverse events	X	X	X	X	X	X	Section 5.2
Vital signs		X			X		Section 3.7.5.3.2
SMWQ	X	X	X	X	X	X	Section 3.7.5.5.1
UDS/alcohol testing via breathalyzer or blood		X			X		Section 3.7.5.2
C-SSRS		X			X		Section 3.7.5.5.2
PHARMACOKINETIC/PHARMACOGENOMIC							
PK blood sample					X		Section 3.7.6.1

^aAll subjects will be required to participate in the 7-day follow-up period (follow-up telephone calls at 1, 3, and 5 days after the last dose of IMP, and in-clinic follow-up visits at 2 and 7 days after the last dose of IMP). Subjects who terminate early, decide to not enroll in Trial 405-201-00015, or who are not eligible to enroll in Trial 405-201-00015, will be required to participate in an additional follow-up telephone call 10 days after the last dose of IMP.

Protocol 405-201-00014

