9.3 Vital Signs

Summary statistics for vital signs will be provided. For the double-blind treatment period vital signs, change from baseline for the double-blind treatment period will be summarized for the Safety Sample by treatment group. Potentially clinically relevant results in vital signs will also be summarized. Similar summaries will be provided for the Safety Sample during the Single-blind Placebo Run-in Period.

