9.7 SMWQ

Medication withdrawal symptoms assessed by SMWQ total scores at the scheduled visits during the double-blind treatment period and follow-up period will be summarized for the Safety Sample by treatment group and overall. The number of patients, mean, median, range and standard deviation will be presented.

9.8 Medication Handling Irregularities (MHIs) and Events Subject to Additional Monitoring (ESAMs)

MHIs and ESAMs will be summarized for the Safety Sample by treatment group and overall. By-patient listings will be provided.

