10.1 Study Visit Windows

Study visit windows will be used to map visits using study day intervals. This visit window convention applies to tables and listings for all efficacy and safety scales (AISRS, CGI-S, AIM-A, ASRS and CGI Change from Baseline). This derived study window variable will be named as DAY and will be footnoted. In listings it will be listed along with the eCRF study visit.

[Table 10-1](#) shows classifications for study day intervals in the double-blind treatment period. The variable “target day” is defined using the number of days since the start of double-blind dosing in the double-blind treatment period. The first day of double-blind dosing is defined as “Day 1”.

If more than one observation falls within a particular study day interval, then the last observation within that interval is used. Evaluations occurring more than three days after the last double-blind dosing date and evaluations occurring during the follow-up period will not be mapped into study visit windows and will be excluded from the double-blind treatment period analysis.

Table 10-1: Study Day and Visit Windows in the Double-Blind Treatment Period

Day	Target Day ^a	Study Day Interval ^a
-----	-------------------------	---------------------------------

SAP 405-201-00014

7	7	2-10
14	14	11-17
21	21	18-24
28	28	25-31
35	35	32-38
42	42	39-49 ^b

^a Relative to the first day of double-blind IMP in the double-blind treatment period.

^b Evaluations occurring more than three days after the last double-blind dosing date and evaluations occurring during the follow-up period will be excluded from the double-blind treatment period analyses.

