10.3.7 Columbia-Suicide Severity Rating Scale (C-SSRS)

Suicidality will be monitored during the trial using the C-SSRS. The C-SSRS is a semi-structured interview that captures the occurrence, severity, and frequency of suicide-related thoughts and behaviors during the assessment period. The interview includes definitions and suggested questions to solicit the type of information needed to determine if a suicide-related thought or behavior has occurred. The interview and rating for the C-SSRS must be completed by a licensed clinician who has been successfully trained to rate this scale by the sponsor or a designee and is medically responsible for the subject. Documentation of trial training should be maintained in the investigational site’s files.

The C-SSRS has a “Screening/Baseline” version, which will be completed at screening and a “Since Last Visit” version that will be completed at all other visits (including the ET visit, if applicable). There are a maximum of 19 items to be completed: 7 required, 10 potential

SAP 405-201-00014

additional items if there is a positive response to a required item, and 2 items for suicide/suicide behavior present during the interview. The C-SSRS uses dichotomous scales (i.e., yes or no), Likert scales, and text or narrative to further describe the thoughts or behaviors.

The C-SSRS is assessed at each scheduled visit in the screening period, the single-blind placebo run-in period, the double-blind treatment period, and at 2 and 7 days after the last dose of IMP in the follow-up period.

SAP 405-201-00014

11 References

- ¹ Siddiqui O, Hung JHM, O'Neill R. MMRM vs. LOCF: A comprehensive comparison based on simulation study and 25 NDA datasets. *J Biopharmaceutical Stats.* 2009; 19(2):227-46.
- ² Diggle P, Kenward MG. Informative drop-out in longitudinal data analysis. *Applied Statistics.* 1994; 43:49-93.
- ³ Little RJA. Pattern-mixture models for multivariate incomplete data. *J Am Stat Assoc.* 1993; 88:125-34.
- ⁴ Little RJA. Modeling the drop-out mechanism in repeated measures studies. *J Am Stat Assoc.* 1995; 90:1112-21.
- ⁵ Hedeker D, Gibbons RD. Application of random effects pattern-mixture models for missing data in longitudinal studies. *Psychological Methods.* 1997; 2:64-78.

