Appendix 1 Criteria for Identifying Vital Signs of Potential Clinical Relevance

Variable	Criterion Value ^a	Change Relative to Baseline ^a
Heart Rate ^b	> 100 bpm < 50 bpm	≥ 10 bpm increase ≥ 10 bpm decrease
Systolic Blood Pressure ^b	≥ 140 mmHg < 90 mmHg	≥ 20 mmHg increase ≥ 20 mmHg decrease
Diastolic Blood Pressure ^b	≥ 90 mmHg < 60 mmHg	≥ 10 mmHg increase ≥ 10 mmHg decrease
Orthostatic Hypotension	≥ 30 mmHg decrease in systolic blood pressure or a ≥ 20 mmHg in diastolic blood pressure after at least 3 minutes of standing compared to the previous supine blood pressure.	Not Applicable (baseline status not considered)
Orthostatic Tachycardia	≥ 25 bpm increase in heart rate from supine to standing	Not Applicable (baseline status not considered)
Weight	-	≥ 7% increase ≥ 7% decrease

^a In order to be identified as potentially clinically relevant, an on-treatment value must meet the “Criterion Value” and also represent a change from the subject’s baseline value of at least the magnitude shown in the “Change Relative to Baseline” column.

^b As defined in “Supplementary Suggestions for Preparing an Integrated Summary of Safety Information in an Original NDA Submission and for Organizing Information in Periodic Safety Updates,” FDA Division of Neuropharmacological Drug Products draft (2/27/87).

SAP 405-201-00014

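### C-SSRS ratings and vital signs taken 2 and 7 days after the last dose enter no planned C-SSRS or vital-sign table or listing; from that week only events recorded as AEs are tabulated

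*SAP*

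**What the plan says.** **Collection.** Protocol section 3.7, Table 3.7-2, marks both the C-SSRS and vital signs at Visits 11 and 14. Its footnote requires all subjects to attend "in-clinic follow-up visits at 2 and 7 days after the last dose of IMP". SAP 10.3.7 repeats the schedule for the C-SSRS: it is rated in screening, run-in, "the double-blind treatment period, and at 2 and 7 days after the last dose of IMP in the follow-up period".

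**Reporting of the C-SSRS.** SAP 9.6 names two periods: "Summary will be provided for the single-blind placebo run-in period and the double-blind treatment period for the Safety Sample". Its definitions of emergent ideation, serious ideation and behavior refer to reports made during treatment.

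**Reporting of vital signs.** SAP 9.3 opens with a general promise of summary statistics and then names the same two periods. For the double-blind period, "change from baseline for the double-blind treatment period will be summarized for the Safety Sample by treatment group". For the run-in, "Similar summaries will be provided for the Safety Sample during the Single-blind Placebo Run-in Period". The footnote to SAP Appendix 1 ties potential clinical relevance to treatment: "an on-treatment value must meet the" stated criterion and also show the stated change from baseline.

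**Measures that do have follow-up reporting.** SAP 9.7 says that SMWQ total scores "at the scheduled visits during the double-blind treatment period and follow-up period will be summarized" (CT-15). The AISRS total and both subscales have follow-up tables (CT-5.2.8, CT-5.3.5, CT-5.3.10). SAP 9.1.1 takes AEs into the summary tables up to 30 days after the last double-blind dose.

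**The concern.** SAP section 3 lists the 7-day follow-up as a fourth period, separate from the double-blind period. A summary limited to run-in and double-blind therefore does not take it in. The result is uneven: the placebo run-in week gets full sets of C-SSRS and vital-sign outputs, and the first week off study drug gets none.

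That week has safety interest of its own. Protocol 1.3 says treatment may be associated with increases in blood pressure and heart rate, and with orthostatic changes. The dosing schedule in Protocol 3.2.2 describes no taper at the end of treatment. Whether blood pressure and heart rate return to baseline, overshoot or stay raised after stopping, and whether ideation appears, are questions these two visits can help answer by arm. If the SAP is followed as written, the systematic part of that answer does not reach the report.

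**Working it through.** There is no sample size, power or alpha figure to reproduce here. The check compares what is collected with what is reported, followed by a count.

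**1. Outputs by period, counted from SAP section 13**

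| Measure | Run-in | Double-blind | Follow-up |
|---|---|---|---|
| Vital signs | 3 (CT-11.3.1 to 11.3.3) | 3 (CT-11.2.1 to 11.2.3) | 0 |
| C-SSRS | 8 (CT-14.2.1 to 14.2.8) | 8 (CT-14.1.1 to 14.1.8) | 0 |

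The counts include listings. The tables whose titles name the follow-up period are CT-5.2.8, CT-5.3.5, CT-5.3.10 and CT-15, and none covers either measure.

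**2. Three kinds of follow-up finding, traced through the SAP**

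- *Ideation rated 4 or 5 at the 2-day visit, none before, not reported as an AE.* SAP 9.6 covers run-in and double-blind only, so it enters no CT-14 table or listing. The C-SSRS section of the protocol (3.7.5.5.2) has no rule that a positive rating must be recorded as an AE. The general AE rules in Protocol section 5 still apply, but the rating itself is not tabulated.
- *A blood pressure or heart rate value at the 2-day visit that meets an Appendix 1 threshold but is not judged clinically significant.* Appendix 1 requires an on-treatment value, and CT-11.2.x covers the double-blind period. It enters no table or listing.
- *A blood pressure or heart rate abnormality at the same visit that the investigator judges clinically significant.* Protocol 3.7.5.3.2 requires it to be recorded as an AE, and SAP 9.1.1 brings it into the TEAE tables. It is captured.

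Mean change after stopping appears in no table, whatever the individual findings.

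**3. Share of scheduled assessments**

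- Double-blind visits with both measures: Days 7, 14, 21, 28, 35 and 42 = 6 (Table 3.7-1).
- Follow-up visits with both measures: 2 (Table 3.7-2).
- Share without a planned output, for a completer: 2 / (6 + 2) = 2/8 = 25%.
- Ceiling, if all 450 randomized subjects attend both visits: 450 × 2 = 900 C-SSRS ratings and 900 sets of vital signs.
- If only the 292 planned completers attend both: 292 × 2 = 584 of each.

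These are counts of scheduled assessments. They do not estimate how many findings would be missed, and the documents give no rate from which to do so.

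**The case against.** - **The AE tables reach into follow-up.** This stands. A reader might infer that suicidality or blood pressure changes after stopping would appear nowhere in the report. The documents do not support that: AEs are collected at every follow-up contact, clinically significant vital-sign abnormalities must be recorded as AEs, and SAP 9.1.1 counts AEs for 30 days. This route depends on individual judgement, however. It cannot show a mean change by arm, and it does not carry C-SSRS ratings as such.
- **The vital-signs gap is an inference.** SAP 9.3 has no restricting sentence like the one in 9.6, and the section 13 list is headed as proposed. It also omits outputs promised elsewhere, such as compliance (6.2) and protocol deviations (6.3). This stands in part. For vital signs the gap is one of omission, so it is less certain than for the C-SSRS, where the body text of 9.6 sets the limit.
- **SAP 10.1 is weak support.** A reader might rely on its rule that "evaluations occurring during the follow-up period will not be mapped into study visit windows and will be excluded from the double-blind treatment period analysis". The scales it names in brackets are the AISRS, CGI-S, AIM-A, ASRS and CGI Change from Baseline. Neither the C-SSRS nor vital signs is among them. The point rests on 9.6, 9.3 and the table list instead.
- **Withdrawal has its own instrument.** The SMWQ is collected on six occasions after the last dose and summarized by arm, so withdrawal is not unreported. It is a symptom questionnaire reported as a total score. It does not show a blood pressure reading, and the SAP derives no suicidality rating from it.
- **The omission is not unique.** Drug and alcohol tests are also scheduled at Visits 11 and 14 and have no listed table.
- **The expected effect is limited.** Protocol 1.3 calls the increases usually modest and asymptomatic. That bears on how often a change would be seen. It is not a reason to leave collected data unsummarized.

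**Conclusion.** The gap is real and limited. C-SSRS and vital-sign assessments 2 and 7 days after the last dose have no planned C-SSRS or vital-sign table or listing, and that week is tabulated only through events recorded as AEs. Three things are lost: C-SSRS ideation or behavior not reported as an AE, mean vital-sign change after stopping, and threshold crossings not judged clinically significant.

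The scale is 25% of a completer's scheduled post-randomization assessments of each kind, with a ceiling of 900 of each. The ceiling assumes full attendance by all 450 subjects. The conclusion assumes that SAP 9.6 is applied as written and that no vital-sign output is produced beyond those named in 9.3 and section 13. Efficacy, alpha, power and trial conduct are unaffected. The SAP should be amended, because the safety account of the off-drug week would otherwise rest on AE reporting and the SMWQ alone.

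**What to change.** In SAP 9.6 and 9.3, add the follow-up period as a separate, descriptive reporting period for the Safety Sample, by randomized arm, at 2 and 7 days after the last dose.

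- **Baseline.** Use the existing double-blind baseline for both measures. For vital signs, also report change from the last on-treatment value, which is the comparison that shows recovery or rebound.
- **C-SSRS definitions.** For these outputs, define emergence and worsening as occurring after the last dose relative to the stated baseline. The emergence definitions in 9.6 cover findings during treatment, so copying CT-14.1.4 to CT-14.1.8 unchanged would not work.
- **Vital-sign criteria.** State that the Appendix 1 thresholds for heart rate, blood pressure and orthostatic change are applied to post-dose values in this period, since the present footnote requires an on-treatment value.
- **Listing.** Add a listing of subjects with new or worsened C-SSRS findings in follow-up.
- **Table list.** Add the corresponding entries to section 13. SAP 10.1 needs no change.

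The cost is SAP wording and a small set of extra descriptive tables. The data are already collected, nothing changes at sites, and no hypothesis test is added.

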9.7 SMWQ

Medication withdrawal symptoms assessed by SMWQ total scores at the scheduled visits during the double-blind treatment period and follow-up period will be summarized for the Safety Sample by treatment group and overall. The number of patients, mean, median, range and standard deviation will be presented.

9.8 Medication Handling Irregularities (MHIs) and Events Subject to Additional Monitoring (ESAMs)

MHIs and ESAMs will be summarized for the Safety Sample by treatment group and overall. By-patient listings will be provided.

9.9 Concomitant Medications

Number and proportion of patients taking concomitant medications prior to the single-blind placebo run-in period, during the single-blind placebo run-in period, during the double-blind treatment period, and after study therapy are tabulated by drug classification using the World Health Organization (WHO) drug dictionary. For the double-blind treatment period Randomized Sample, data will be presented by treatment group and overall.

SAP 405-201-00014

9.10 Extent of Exposure

The start date of double-blind IMP - centanafadine or placebo - will be the first day of double-blind dosing. The number and percentage of subjects who receive double-blind IMP, will be presented by week and by treatment group. Each dosing week will be based on the actual week; i.e., Day 1-7 in Week 1, Day 8-14 in Week 2, etc. This summary will be performed on the Safety Sample.

The mean daily dosage will be summarized by week and treatment group using descriptive statistics. The mean daily dosage per subject per week will be determined for each week of the study. This will be calculated by dividing the sum of individual total doses by the number of days in the week interval. The summary will contain for each treatment group the number of patients receiving double-blind IMP, and the mean and range of the mean daily dose for each week.

10 Conventions

10.1 Study Visit Windows

Study visit windows will be used to map visits using study day intervals. This visit window convention applies to tables and listings for all efficacy and safety scales (AISRS, CGI-S, AIM-A, ASRS and CGI Change from Baseline). This derived study window variable will be named as DAY and will be footnoted. In listings it will be listed along with the eCRF study visit.

[Table 10-1](#) shows classifications for study day intervals in the double-blind treatment period. The variable “target day” is defined using the number of days since the start of double-blind dosing in the double-blind treatment period. The first day of double-blind dosing is defined as “Day 1”.

If more than one observation falls within a particular study day interval, then the last observation within that interval is used. Evaluations occurring more than three days after the last double-blind dosing date and evaluations occurring during the follow-up period will not be mapped into study visit windows and will be excluded from the double-blind treatment period analysis.

Table 10-1: Study Day and Visit Windows in the Double-Blind Treatment Period

Day	Target Day ^a	Study Day Interval ^a
-----	-------------------------	---------------------------------

SAP 405-201-00014

7	7	2-10
14	14	11-17
21	21	18-24
28	28	25-31
35	35	32-38
42	42	39-49 ^b

^a Relative to the first day of double-blind IMP in the double-blind treatment period.

^b Evaluations occurring more than three days after the last double-blind dosing date and evaluations occurring during the follow-up period will be excluded from the double-blind treatment period analyses.

10.2 Pooling of small centers

Primary efficacy analysis will be performed on the Efficacy Sample which comprises those subjects in the Randomized Sample who have a baseline value for the double-blind treatment period and at least one post-randomization value for AISRS total score in the double-blind treatment period. Small centers will be defined as centers that do not have at least one evaluable subject (evaluable with regard to the primary efficacy variable) in each treatment arm in the double-blind treatment period. All small centers will be pooled to form “pseudo centers” for the purpose of analysis according to the following algorithm. Small centers will be ordered from the largest to the smallest based on the number of evaluable subjects (i.e., subjects who have a baseline value for the double-blind treatment period value and at least one post-randomization value for AISRS total score in the double-blind treatment period). The process will start by pooling the largest of the small centers with the smallest of the small centers until a non-small center is formed. This process will be repeated using the centers left out of the previous pass. In case of ties in center size, the center with the smallest center code will be selected. If any centers are left out at the end of this process, they will be pooled with the smallest pseudo centers, or if no pseudo centers exist, they will be pooled with the smallest non-small center.

